HALT-C Ancillary Study PROPOSAL

PART I

Proposal Name: Application of Novel Organ-Specific Serum Protein Biomarker Candidates to Diagnose Hepatic Fibrosis in Hepatitis C Patients in HALT-C Trial

Proposal PI: [name]

Co-Investigators: [name], Institute for Systems Biology, Seattle; [name], Institute for Systems Biology, Seattle, WA; [name] and [name], University of Michigan

HALT-C PI: [name], University of Michigan

Funding Agency and Review Body (e.g., NIDDK; my university/GAC): Luxembourg Ministries of Health, Research, and Economy and External Trade. Funding announced in July 2008.

I agree to follow HALT-C Policies and Procedures when conducting this study. I acknowledge that the data obtained from this study will belong to the NIH and will be placed in the HALT-C database for use by other investigators. I understand that I cannot begin experiments using HALT-C specimens/data until I receive approval from the HALT-C Ancillary Studies Committee and funding from the Scientific Review Body for my proposal. I also understand that the data analysis for this proposal will be performed by NERI (unless otherwise approved by the HALT-C study) and that Protocols approved by the HALT-C Ancillary Studies Committee will be placed on the HALT-C Restricted Website.

Proposal Principal Investigator

Date

HALT-C Principal Investigator

Date

PART II: PROTOCOL

1. Hypothesis: Organ-specific proteins can be detected in the circulation and can be used to monitor disease-specific changes in the primary organ affected, namely liver for hepatic fibrosis and its progression.

Background: The ISB investigators have utilized findings from highly sensitive transcriptomic analyses with massively parallel signature sequencing and next-generation high throughput sequencing and from proteomics analyses (multiple reaction monitoring (MRM); unique N-glycopeptides) to identify liver-specific protein biomarker candidates detectable in plasma.

Specific Aim 1, Pilot Phase: Use panels of liver-specific protein biomarker candidates in high-throughput format with HALT-C specimens in a preliminary study to determine whether these markers can distinguish patients with cirrhosis from those with fibrosis. Liver biopsy specimens and serum specimens collected at the same time from such patients will be tested to relate protein changes in liver to homologous protein changes in serum.

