Specific Aim 2: Validate serum biomarker findings from Aim 1 in a larger number of HALT-C specimens (independent of those used in Aim 1) to evaluate usefulness of this panel in identifying patients with cirrhosis and in predicting which patients will have disease progression.

2. Background/Rationale: Systems Biology with Blood Protein Fingerprints as Disease Diagnostics

2.1 Blood is a window into the status of the body's health. Organs throughout the body are highly dependent upon a continuous supply of energy through the circulatory system and for removal of molecules and cells released in health and disease. Blood is an informative specimen window to assess the functional status of organs, detect biological responses of organs to injuries, and monitor specific markers of developing pathology. In this project, we will explore and validate a panel of blood- and tissue-based liver-specific markers, including both RNA and proteins during the progression of HCV-related diseases.

2.2 Organ-specific blood molecular fingerprints. Uncertainty about the tissue of origin of protein biomarker candidates causes diagnostic non-specificity. The solution is to identify and utilize organ-specific biomarkers (majority of the message produced normally by only one organ). To identify organ-specific markers, we have used two different, complementary datasets: (a) a deep (millions of transcripts for each organ) transcript database generated at the Institute for Systems Biology using a technique called massively parallel signature sequencing (MPSS), and (b) data from a microarray platform containing over 42,000 different cDNA clones, from the National Cancer Institute (NCI). The MPSS dataset contains transcripts from 37 distinct human tissues, including replicate data for 7 of these tissues and 13 from perturbations of the normal state of these tissues [[name] et al, 2004]. The NCI microarray dataset contains expression results of 19 different human organs with 158 normal human samples obtained from 30 different individuals [Son et al, 2005]. Since the analyzed data are not available from NCI, we downloaded the entire dataset, reanalyzed with specific selection criteria (e.g., that 50% of the expression signals come from particular tissues), and extracted tissue "specific" genes (see Figure 1).

[figure not shown]
[figure not shown]

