2.4 The development of MRM peptides for liver-specific proteins. From liver-specific transcripts, we selected 36 proteins as highly specific for liver and known to be detectable in plasma, since they were reported already in the Human Proteome Organization (HUPO) international Plasma Proteome Project led by [name], [name], and [name] and in the PeptideAtlas database (www.peptideatlas.org, [name], ISB). Based on this list of proteins (Table 1), we have designed peptide standards for MRM assays, at least two per protein for most of the proteins. These peptides are unique or highly associated with the particular protein, and are designed to be detectable in the mass spectrometer and quantifiable [Anderson & Hunter, 2006]. These prepared peptides have been extensively tested on Thermo Finnigan LCQ deca instruments with full LC-MS/MS and SRM (selected reaction monitoring) runs. The current list of MRM peptides for liver-specific proteins is included below (Table 1, at end).

Based on the results, MRM transition candidates from each parent peptide standard ion were selected and tested for MRM analysis. We have developed MRM methods to scout several precursor-fragment ion transition pairs from each peptide over a large time period in order to observe elution for each peptide on a Waters nanoAcquity UPLC system coupled to a Waters Quattro Premier XE triple quadrupole mass spectrometer or an Eksigent Tempo nano-LC system coupled to an ABI Q-Trap 4000 mass spectrometer. These observed retention times will be mapped to a time-segmented MRM method capable of analyzing hundreds of peptide precursor-fragment ion transition pairs in a single chromatographic run. Results for peptide standards were obtained that show capturing of transition daughter ions with reasonably strong signals. We create a liver-specific fingerprint by comparing the isotopically-labeled (heavy) peptide standards to endogenous (light) blood protein in mouse or human.

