We will compare expression levels of the organ-specific proteins in the two groups of patients, using a cross-sectional design. Longitudinal progression within individual patients will be left for Specific Aim 2. Given the complications of sampling error for each phenotype, the preferred design is cross-sectional, informed by knowledge that the patients with fibrosis did not progress to cirrhosis on follow-up biopsies, allowing clear separation of the groups.

Sample Size. For this pilot study, we plan the sample size to detect a relative difference of 40% in protein levels between any two groups of patients in the pairwise comparisons between fibrosis and cirrhosis. Assuming a coefficient of variation of <0.5 , we would have at least 80% power to detect the difference with 20 patients per group.

Statistical Analysis Plan. Multiple linear regression will be used to assess the effects of candidate liver-specific proteins associated with the list of MRM peptides. Transformations will be considered should model diagnostics plots reveal any evidence of departure from linearity. In a secondary analysis, we will reverse the problem formulation with the disease category (fibrosis, cirrhosis, HCC) being the response while protein expression levels are the explanatory variables. Due to small sample size, principal component analysis on protein expression will be used to reduce the dimension of the feature vector with the first two/three principal components entering a multinomial logistic regression model. Since data are sampled based on the disease status, no prediction of absolute probabilities of the type of disease based on the protein level will be attempted. The focus will be on identifying significant relative effects potentially allowing us to discriminate between the pairs of disease categories.

4.2 Specific Aim 2, Validation Study: Validate serum biomarker findings from Aim 1 in a larger number of HALT-C specimens (independent of those used in Aim 1) to evaluate usefulness of this panel in the diagnosis of hepatitis C-related cirrhosis and in the prediction of progression of liver disease.

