Statistical Analysis Plan: As for Aim 1, we will use multiple linear regression with the disease status as a categorical covariate. Adjusted R-Squared, Mallow's Cp, and AIC criteria will be used to ensure reproducibility of the predictive properties of the protein panel in future observations. In order to handle multiple observations made on a subset of study subjects, a random intercept term will be introduced in the linear mixed model. As a secondary analysis, survival analysis methods (proportional and non-proportional hazards regression models) will be used on a subset of subjects with follow-up information on their progression from fibrosis to cirrhosis and/or HCC during the follow-up. There is insufficient information at this point to assess the power and precision of the validation analysis. Therefore, updated sample size assessment will be performed after Aim 1 has been completed, yielding quantitative data on coefficient of variation and on group differences by protein. Tentatively, using the same assumptions as in Aim 1, we expect to have improved sensitivity with 30 patients per group, instead of 20, resulting in an ability to detect a 27% difference in protein levels. We will analyze both individual proteins and all proteins, as well as potentially related, clustered proteins as secondary analyses.

5. Methods & Data Usage

a) Novel technology platforms: Next generation deep sequencing for transcripts (such as Solexa); N-glycopeptide proteomics and multiple reaction monitoring for proteins by mass spectrometry.

b) Protein biomarker panel: See Table 1 for proteins and MRM peptides to be assayed.

c) Assays of liver and serum specimens: We will use multiple reaction monitoring of the 2 or 3 specific peptides associated with each of the 36 proteins in the Table below in an Orbitrap or LTQ-FT mass spectrometer; the peptides have already been designed (Table 1).

d) Statistical design and analysis: See specific sections under Aim 1 and Aim 2.

e) Data usage: We will fully comply with the HALT-C Data Use Agreement. Samples will be labeled with HALT-C subject no. and sample ID. We have no interest in specific-patient identifiers. We will use newly-generated identifiers held by the HALT-C PI to permit longitudinal analyses of serum specimens from the patients studied. We will report all findings on a group basis.

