To address Aim 1, a defined data set on patients whose samples are studied will be created by NERI and sent to University of Michigan (or Institute of Systems Biology) for analysis. The dataset will include:

- Demographics, duration of HCV infection, alcohol and smoking history, BMI, HCV genotype
- Baseline information: histology (date of biopsy, inflammation, fibrosis and steatosis score, length of biopsy and fragmentation), baseline labs (date of labs, CBC, liver panel, Cr, INR, AFP, HCV RNA), baseline ultrasound (date of ultrasound or other imaging, spleen size), baseline EGD (date of EGD, presence or absence of esophageal varices / portal gastropathy)
- Month 24 information: histology (date of biopsy, inflammation, fibrosis and steatosis score, length of biopsy and fragmentation), labs (date of labs, CBC, liver panel, Cr, INR, AFP, HCV RNA), ultrasound (date of ultrasound or other imaging, spleen size)
- Month 48 information: histology (date of biopsy, inflammation, fibrosis and steatosis score, length of biopsy and fragmentation), labs (date of labs, CBC, liver panel, Cr, INR, AFP, HCV RNA), ultrasound (date of ultrasound or other imaging, spleen size), EGD (date of EGD, presence or absence of esophageal varices / portal gastropathy)
- Information at last follow-up: labs (date of labs, CBC, liver panel, Cr, INR, AFP, HCV RNA), ultrasound (date of ultrasound or other imaging, spleen size)
- Treatment assignment: peginterferon vs. control, for peginterferon group – date of last dose
- Occurrence of clinical outcomes: date when each outcome is reached

6. Anticipated Results

a) We are confident that the new technology platforms and powerful transcriptomic and proteomic assays will be shown to identify organ-specific proteins for liver detectable in serum.

b) We expect to generate novel protein biomarkers that differentiate progressors from non-progressors among hepatitis C patients in HALT-C trials.

c) We will test in Aim 2 whether serum levels of these protein biomarkers can differentiate and predict progression to cirrhosis and clinical decompensation. We hope to provide new biomarker assays for the non-invasive assessment of liver fibrosis and disease progression to HALT-C investigators.

7. Statistical Support

[name] has obtained consulting statistical guidance from [name], Professor of Biostatistics at the University of Michigan and Affiliate Faculty in the Center for Computational Medicine and Biology.

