glycine N-methyltransferase	NP_061833.1	3	AWLLGLLR VWQLYIGDTR SLGVAEGLDQYADGEAAR
argininosuccinate synthetase 1	NP_446464.1	2	BQGYDVIAYLANIGQK GQVYILGR
4-hydroxyphenylpyruvate dioxygenase	NP_002141.1	3	FLHFHSVTFWVGNAAK GYLLQIFTK TEDIITAIR
argininosuccinate lyase	NP_000039.2	3	WSHWILSHAVLTR FVGAVDPIMEK VAEWAQGTF GIVVGIK
aldolase B, fructose-bisphosphate	NM_000035.2	3	ALNDHHVYLEGTLK DGVDFGK
betaine-homocysteine methyltransferase	NP_001704.2	2	VNEAACDIAR AIARELAPER
homogentisate 1,2-dioxygenase	NP_000178.2	2	LLIYTFGK CFYNSDGDPLIVPQK
beta-carotene 15, 15'-monooxygenase 1	NP_059125.2	2	FAVPLHVDK YVFATGVQWSPITPK
glutamate dehydrogenase 1	NP_005262.1	2	YSTDVSDEVK MVEGFFDR
catalase	NP_001743.1	2	HMNGYGSHTFK FYTEDGNWDLVGNNTPIFFIR
retinol-binding protein 4	NP_006735.2	2	YWGVSFLQK FSGTWAMAK
fibrinogen-like 1	NP_004458.3	3	SDGENFNR FSTWDR AQVRLLETR
fructose-1,6-bisphosphatase 1	NP_000498.2	2	TLVYGGIFLYPANK DFDPAVTEYIQK
methionine adenosyltransferase I, alpha	NP_000420.1	3	FVIGGPQDAGVTGR YLEDFTVYHLQPSGR FVIGGPQDAGLTGR
hydroxyacid oxidase 1	NP_060015.1	2	AIFVTVDTPYLGNR LAMALSGCQNVK
aldehyde dehydrogenase 1A1	NP_000680.2	2	IFINNEWHDSVSGK VAFTGSTVEGK
isocitrate dehydrogenase 1	NP_005887.2	2	TVEEAAHGTVTR LIDDMVAQAMK
proteasome alpha 2 subunit	NP_002778.1	2	YNEDLEDAIHTAILTLK HIGLVYSGMSPDYR
DNA directed RNA polymerase II polypeptide B	NP_000929.1	2	MTIHLIECLQK DCQIAGHAAQFLR
glutamate-ammonia Ligase	NP_002056.2	1	DIVEAHYR
asialoglycoprotein receptor 1	NP_001662	1	LLHVK
Asialoglycoprotein receptor 2	NP_550434	2	WVDGTDYR ADHDALLFHLK
Carbamoyl-phosphate synthetase 1, mitochondrial	NP_001866	1	GNDVLVIECNLR LSIQCYLR
3-hydroxy-3-methylglutaryl-Coenzyme A synthase 2	NP_005509	3	YTVGLGQTR VSFEFTEIMNQR SHTGLGR
Transferrin	NP_001054	3	DQYELLCNDTR TAGMNIWGLLYNK TPENFCK
Plasminogen	NP_000292	3	EAQLPVIENK HSIPTETNDR DFHINLFQVLPWLK
complement factor B preproprotein	NP_001701	2	GDSGGPLIVHK IHVYEK
paraoxonase 1	NP_000437	2	HANWTLTPLK IYHSHIDAPK
ceruloplasmin precursor	NP_000087	2	TYCSEPEK SHIAQNSPHTPPR
Interleukin 6 signal transducer	NP_002175	2	HQVPSVQVFSR DFTVLVDR
Peroxisome biogenesis factor 1	NP_000457.1	2	GFLPASLR
Importin 4	NP_078934.3	2	ACYALENFVENLGGPK LLPPLLIQVCK
Purine nucleotide phosphorylase	NP_000261.2	2	FEVGDIMLIR VGFSLITNK ENFSCLTR
Malate dehydrogenase	NP_005908.1	2	LSSAMSAK

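### The stated protein models do not include the biopsy inflammation score, so if the groups differ in inflammation, a marker of liver-cell injury could be read as a marker of fibrosis

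*Protocol*

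**What the plan says.** The hypothesis in Protocol Part II, section 1 is that organ-specific proteins in the circulation "can be used to monitor disease-specific changes in the primary organ affected, namely liver for hepatic fibrosis and its progression". Section 2.4 states the basis for the candidates: "we selected 36 proteins as highly specific for liver and known to be detectable in plasma". They are listed in Table 1.

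Section 4.1 sets the Aim 1 comparison: "We will compare expression levels of the organ-specific proteins in the two groups of patients, using a cross-sectional design". It specifies multiple linear regression and names no adjustment covariate. For Aim 2, section 4.2 says "we will use multiple linear regression with the disease status as a categorical covariate" and adds a random intercept for repeated samples. Matching in Aim 2 is described as desirable and covers gender, ethnicity and HCV genotype.

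Section 5e lists the data to be sent for analysis, including "Baseline information: histology (date of biopsy, inflammation, fibrosis and steatosis score, length of biopsy and fragmentation". That dataset is requested to address Aim 1; no dataset is listed for Aim 2. Section 7 says the statistical analysis plans are those given under the two aims.

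**The concern.** Most of the candidates are metabolic enzymes or other proteins that work inside the cell. Only one row of Table 1 names a compartment ("Carbamoyl-phosphate synthetase 1, mitochondrial"), but the protein names generally make the class clear. Such proteins may appear in serum because hepatocytes are being damaged, as transaminases do, and not because scar has formed. The Protocol recognises the route in general terms: section 2.1 says blood can be used to "detect biological responses of organs to injuries".

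The two Aim 1 groups are chosen to be far apart: bridging fibrosis without any outcome, and cirrhosis with later decompensation. They may also differ in necroinflammatory activity. If they do, a comparison containing disease status alone cannot tell activity from fibrosis, which is the distinction the hypothesis needs. Aim 1 also determines which proteins form the panel, and Aim 2 states the same kind of model, so an imbalance that persisted would be carried into validation.

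**Working it through.** **Inputs from the Protocol.** 36 candidates (section 2.4; Table 1 also has 36 rows); 20 patients per group, a 40% difference and a coefficient of variation below 0.5 (section 4.1).

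**The plan's own figure.** 0.40 / 0.5 = 0.8 SD. With 20 per group and a normal approximation, power is 81.2% for a one-sided 5% test and 71.6% for a two-sided one. The stated figure of at least 80% is therefore reproduced one-sided. It is not disputed here and serves only to give the scale of the planned effect.

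**Count by protein name.** 26 intracellular; 7 secreted (retinol-binding protein 4, fibrinogen-like 1, transferrin, plasminogen, complement factor B, paraoxonase 1, ceruloplasmin); 3 membrane receptors (asialoglycoprotein receptors 1 and 2, interleukin 6 signal transducer). 26 + 7 + 3 = 36, and 26/36 = 72%.

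**Assumptions not in the documents.** r is the within-group correlation of a serum protein with the inflammation score. g is the group difference in that score, in SD. The test is two-sided at 5%; the Protocol states neither the level nor the sidedness.

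**Formula.** A protein with no fibrosis effect shows a group shift of r × g SD. The two-sample t-test has 38 degrees of freedom and non-centrality r × g × √(20/2).

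| g | r | shift r × g (SD) | non-centrality | rejection rate |
|---|---|---|---|---|
| 0 | any | 0 | 0 | 5.0% |
| 0.5 | 0.3 | 0.15 | 0.47 | 7.5% |
| 0.5 | 0.5 | 0.25 | 0.79 | 12.0% |
| 0.5 | 0.7 | 0.35 | 1.11 | 19.0% |
| 0.8 | 0.3 | 0.24 | 0.76 | 11.5% |
| 0.8 | 0.5 | 0.40 | 1.26 | 23.4% |
| 0.8 | 0.7 | 0.56 | 1.77 | 40.8% |

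A simulation with 20,000 runs per cell gave the same unadjusted rates to within sampling error (7.4% to 40.7% over g = 0.5 to 0.8). With the score in the model the rate was 4.6% to 5.1% over all settings tried (g from 0 to 1.0), for a score measured without error.

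**Scale.** At a coefficient of variation of 0.5, shifts of 0.15 to 0.56 SD are 0.15 × 0.5 = 7.5% to 0.56 × 0.5 = 28% of the mean, against the planned 40%. If all 26 intracellular proteins were pure injury markers, the expected number declared significant would be 26 × 0.075 = 1.9 to 26 × 0.408 = 10.6, against 26 × 0.05 = 1.3 with balanced groups.

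**Price of adjusting.** For a true 0.8 SD effect, the unadjusted t-test has 69.3% power with balanced groups. The adjusted model has 72% to 93% at g = 0 and 66% to 91% over g = 0.5 to 0.8, for r = 0.3 to 0.7. Adjustment gains precision when the groups are balanced and can lose some when group and inflammation are correlated.

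**The case against.** The strongest reply is that the aims concern discrimination and prediction, and that the go rule for Aim 2 is panel accuracy of at least 70%. For that purpose the unadjusted difference is the right quantity: a marker that separates the groups partly through injury still separates them. This stands. The rates above are false positives only for the claim that a protein reflects fibrosis, which the section 1 hypothesis makes but the go rule does not test.

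A reader might infer that inflammation alone could carry the panel past the go rule. The figures do not support that in the range considered. With two equal groups the accuracy is Φ(shift/2), which is 53% at 0.15 SD and 61% at 0.56 SD for a single marker. A score tracking inflammation perfectly reaches 66% at g = 0.8 and needs g of about 1.05 to reach 70%, leaving aside any optimism from fitting and testing on the same patients.

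The Protocol also has partial checks. Section 2.4 plans a comparison with SGOT, SGPT and GGT, and section 4.1 first relates protein changes in liver to those in serum. Both bear on leakage, but neither enters a model or carries a stated criterion.

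It can be said that multiple linear regression leaves room for covariates, that disease status is not called the only one, and that such lists often wait for a separate plan. The text does not rule adjustment out. But section 7 places the analysis plans in the two aims, and those name no inflammation term.

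Finally, the compartments are read from protein names, and no group difference in inflammation is documented. Both limits stand, and they are why the consequence is conditional.

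**Conclusion.** The point holds as a conditional one. The stated models leave out a baseline variable that is already requested for Aim 1 and that bears on whether a group difference can be attributed to fibrosis. Under the assumed ranges (r 0.3 to 0.7, g 0.5 to 0.8, two-sided 5%, 20 per group) the per-protein false-positive rate for a fibrosis effect is about 7% to 41%. At g = 0 it is 5% and there is no bias.

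Three stronger readings are tempting and not supported. First, a reader might infer that most of the candidate list will shift together and be misread; the documents show no imbalance and no correlation. Second, a reader might infer that a protein should be called a fibrosis marker only if its adjusted effect stays significant. With 20 per group, serum up to 90 days from the biopsy, and sampling error that section 4.1 itself acknowledges, loss of significance is weak evidence, and inflammation may lie on the pathway to progression. Third, a reader might infer that the score is already available for both aims; section 5e requests it for Aim 1 only. Nor is there a worked case for adding the steatosis score.

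**What to change.** In section 4.1, prespecify that each baseline protein model is fitted with and without the baseline biopsy inflammation score, and that both disease-status effects are reported with confidence intervals. State the same in section 4.2, and extend the section 5e data request so that the score is supplied for the Aim 2 patients.

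Keep the unadjusted result and the panel accuracy for the discrimination aim and the 70% go rule. Use the adjusted estimate to qualify any statement that a protein reflects fibrosis rather than activity, and say in advance that non-significance after adjustment does not by itself count as failure.

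The cost is a few sentences, one extra data item for Aim 2 and one degree of freedom per model. Some power may be lost where inflammation and group are correlated. Adjustment will be incomplete because the score is noisy, and for the progression question it may remove part of a real effect, which is why both estimates should be shown.

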We will interrogate protein level changes with disease phenotypes in samples spiked with isotopically labeled peptide standards. We will also search the transcript, proteome, and peptide databases for known liver markers: AFP (alpha-fetoprotein), N-fucosylated AFP-L3, DCP (des-gamma carboxyprothrombin), Glypican 3, GP73 and N-fucosylated GP73, GEP (granulin-epithelin precursor), and mortalin [Block et al, 2008]. We will compare with standard liver function assays for SGOT, SGPT, and GGT transaminase activity. In all of these cases, we will explore the feasibility of MRM peptide standards.

3. Relation to Aims of HALT-C Study

This ancillary study is closely related to the aims of HALT-C as the goal is to develop and evaluate non-invasive tests for diagnosis of fibrosis and progression of liver disease. If the organ-specific markers, defined

with both mRNA and protein studies of the liver, can be linked with organ-specific proteins in the circulation, we may be able to diagnose cirrhosis and progressive liver disease non-invasively.

4. Study design, experimental groups

4.1 Specific Aim 1: Use panels of liver-specific protein biomarker candidates in high-throughput format with HALT-C specimens in a preliminary study to determine whether these markers can distinguish hepatitis C patients with cirrhosis versus fibrosis. Liver biopsy specimens and serum specimens collected as close as feasible to the same time from such patients will be tested to relate protein changes in liver to homologous protein changes in serum.

We request baseline liver biopsy specimens and serum specimens within 90 days from 20 patients with Ishak 3 or 4 (bridging fibrosis) who did not have histological or clinical outcome during the course of the study and 20 patients with cirrhosis who developed clinical decompensation during the study. We will first document what protein changes in liver can be related to and account for homologous protein changes in serum among the 36 proteins in Table 1 and any others added with the same criteria of liver-specific transcripts and detectability and quantifiability in serum.

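### The Aim 1 claim of at least 80% power for a 40% difference with 20 per group does not hold at the CV bound for a conventional two-sided 5% test, and the figure is per protein

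*Protocol*

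**What the plan says.** The sample-size paragraph of Protocol Section 4.1 sets the target: "we plan the sample size to detect a relative difference of 40% in protein levels between any two groups of patients". It adds a variability condition, "Assuming a coefficient of variation of <0.5", and concludes "we would have at least 80% power to detect the difference with 20 patients per group". The two groups are 20 patients with Ishak 3 or 4 and no outcome, and "20 patients with cirrhosis who developed clinical decompensation during the study".

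The paragraph gives no significance level and does not say whether the test is one- or two-sided. It does not say which group's mean the 40% and the CV refer to, whether the difference is a rise or a fall, or whether levels are compared raw or on the log scale. The analysis paragraph that follows plans linear regression and leaves the scale open: "Transformations will be considered should model diagnostics plots reveal any evidence of departure from linearity".

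Section 4.1 also says how many proteins are examined: "homologous protein changes in serum among the 36 proteins in Table 1 and any others added". The sample-size paragraph does not mention that number.

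**The concern.** A 40% difference with a CV of 0.5 is a standardised difference of 0.8. With 20 per group, the usual two-sided 5% test has clearly less than 80% power for an effect of that size. The protocol says at least 80% and bounds the CV at 0.5, so the statement should stay true up to that bound.

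This sentence is the protocol's only justification for 20 patients per group. The panel carried into Aim 2 is assembled from Aim 1 results (Section 4.2), so a protein overlooked in Aim 1 may not be recovered later. Section 4.2 also takes over the Aim 1 assumptions for its tentative sample size. A reader who takes 80% at face value will read a null result for a protein as stronger evidence than it is, most of all for proteins that are higher in the comparison group than in the reference group.

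**Working it through.** **Inputs from Protocol Section 4.1:** relative difference 0.40; CV taken at its bound, 0.5; n = 20 per group; 36 proteins.

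**Assumptions, because the protocol is silent:** alpha 0.05, one- and two-sided; 0.05/36 as an illustration only.

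**Method:** two-sample t test, df = 2 × 20 − 2 = 38. Noncentrality = d × √(n/2) = d × √10 = 3.162 d. Critical values are 2.024 (two-sided 5%), 1.686 (one-sided 5%) and 3.450 (two-sided 0.05/36). Power comes from the noncentral t distribution.

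**Reproducing the plan's figure.** Take the reference mean as 1 and a common SD of 0.5, so d = 0.40/0.50 = 0.80. The one-sided 5% normal approximation gives n = 2 × (1.645 + 0.842)² / 0.80² = 19.3, rounded up to 20 per group, with power 81%. The noncentral t gives 79.9%. So the stated figure can be reproduced one-sided on a common SD.

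**Standardised difference under each reading:**
- Common SD: d = 0.40/0.50 = 0.800.
- 40% rise, constant CV: SDs 0.5 and 0.7, pooled √((0.25 + 0.49)/2) = 0.608, d = 0.658.
- 40% fall, constant CV: SDs 0.5 and 0.3, pooled √((0.25 + 0.09)/2) = 0.412, d = 0.970.
- Log scale: SD = √ln(1 + 0.5²) = 0.472. Rise: d = ln(1.4)/0.472 = 0.712. Fall: d = −ln(0.6)/0.472 = 1.081.

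**Power at n = 20 per group, CV = 0.5 (noncentral t):**

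| Reading | d | Two-sided 5% | One-sided 5% | Two-sided 0.05/36 |
|---|---|---|---|---|
| Common SD | 0.800 | 69.3% | 79.9% | 20% |
| 40% rise, constant CV | 0.658 | 52.7% | 65.4% | 10% |
| 40% rise, log scale | 0.712 | 59.3% | 71.5% | 14% |
| 40% fall, constant CV | 0.970 | 84.8% | 91.4% | 37% |
| 40% fall, log scale | 1.081 | 91.5% | 95.7% | 50% |

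**What two-sided 80% power would require.** On a common SD: 26 per group at CV 0.5, or CV ≤ 0.44 at 20 per group. For a 40% rise at 20 per group: CV ≤ 0.36 with constant CV, or ≤ 0.38 on the log scale.

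**Detectable difference at n = 20, CV 0.5, two-sided 5%, 80% power.** The required d is 0.909. Raw scale, common SD: 0.909 × 0.5 = 0.455, about 45%. Log scale: a fall of 1 − exp(−0.909 × 0.472) = 35%, or a rise of exp(0.909 × 0.472) − 1 = 54%.

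**The case against.** The strongest reply is that the sentence is underspecified rather than miscalculated. One-sided at 5% on a common SD, the normal approximation needs exactly 20 per group. The protocol also says the CV is below 0.5, not equal to it: at 0.499 the one-sided noncentral-t power is already 80.1%. With the higher group as reference, the same gap is a 40% fall whichever group is higher, and two-sided power is then 85% to 91% with constant CV or on the log scale. All of this stands, and it limits the finding. What remains is that the protocol adopts none of these readings, and a screen of many proteins with no stated direction is naturally two-sided.

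A reader might infer more in two places, and the protocol does not support either.

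- **That every 40% rise is underpowered.** On a common SD direction makes no difference, and one-sided power for a rise is the same 80%. The shortfall specific to rises needs constant CV or a log scale, with the lower group as reference.
- **That about two false markers will enter the panel.** Testing 36 independent null proteins at 5% gives 36 × 0.05 = 1.8 expected false positives and a chance of at least one of 1 − 0.95³⁶ = 84%. But nowhere does the protocol select proteins by unadjusted p < 0.05. The sentence "The focus will be on identifying significant relative effects potentially allowing us to discriminate between the pairs of disease categories" closes the secondary analysis, which enters two or three principal components into a multinomial model and is not 36 separate tests. Aim 2 proceeds only if panel accuracy is at least 70% (Section 4.2) and the ancillary studies committee has reviewed the results (Part III), and it uses independent specimens.

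The choice of multiplicity procedure could properly sit in a separate analysis plan, so its absence here is not an error. The power sentence itself is in the protocol, and it can say that it refers to a single protein.

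**Conclusion.** The concern holds in limited form. At the CV bound, a two-sided 5% test with 20 per group has about 69% power for a 40% difference on a common SD, roughly 11 percentage points below the claim. For a 40% rise it has 53% (constant CV) or 59% (log scale). The claim of at least 80% is true for a one-sided 5% test on a common SD (to rounding), for a 40% fall, or for a CV of about 0.44 or less on a common SD.

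The figure also makes no allowance for 36 proteins. At the illustrative 0.05/36 level, two-sided power is 20% on a common SD and no more than 50% under any reading tried.

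The conclusion rests on an assumed alpha of 0.05 and a two-sided test, neither of which the protocol states. The 0.05/36 level is likewise illustrative. Severity is moderate: this is a pilot, the gate to Aim 2 does not use the power figure, and validation uses independent specimens.

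**What to change.** Restate the sample-size sentence in Section 4.1 with alpha, sidedness, scale and reference group, and give figures that belong to the chosen scale. For a two-sided 5% test with CV 0.5 and 20 per group:

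- **Raw scale, common SD:** about 69% power for a 40% difference, or 80% power for about a 45% difference.
- **Log scale:** 80% power for about a 35% fall or a 54% rise; for 40%, about 91% power for a fall and 59% for a rise.

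The two sets should not be mixed. If the team did intend a one-sided test, or a CV of 0.44 or less, it should say so and why. Add that the power is per protein, before any multiplicity control. The multiplicity method can be left to the analysis plan. Section 4.2 borrows the Aim 1 assumptions, so its tentative figure should be checked against the restated ones.

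The cost is a wording change and a less favourable stated figure. No extra patients or specimens are needed.
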